5.6.1.1. Intervention Compliance

Compliance calculation is not applicable for this study.

Relevant deviations from the dosing schedules will be documented through major protocol deviations. See the Major Protocol Deviation Criteria document for this study.

Exposure to study intervention is described in section 5.6.1.

5.6.2. Adverse Events

See section 5.3.2

5.6.3. Additional Safety Assessments

5.6.3.1. Clinical Laboratory Tests

Clinically significantly abnormal laboratory results are recorded as an AE and will be reported in Section 5.3.2.

5.6.3.2. Vital Signs and Physical Examination Findings

Continuous vital sign parameters including weight, respiratory rate, pulse, and blood pressure (systolic and diastolic) will be summarized at each assessment time point. If the time point (predose/post-dose) is missing, this will be derived from the vital sign assessment time and the esketamine administration time. Change from baseline in Study 54135419TRD3013 will be summarized. Descriptive statistics (mean, SD, median, minimum and maximum) will be presented.

In addition, descriptive statistics of pre-dose and post-dose pulse rate, blood pressure (systolic and diastolic) values and respiratory rate, and changes from pre-dose will be provided for each intranasal dosing day.

Abnormality criteria (based on criteria defined below) will be applied to baseline and postbaseline post-dose values. For baseline values, increase or decrease criteria are not applied.

Postbaseline values will be considered treatment-emergent if they meet both value and change criteria in the table below.

For criteria that do not include an increase or decrease from baseline:

- Treatment-emergent will be concluded if the postbaseline value is above the upper limit and the baseline value is below the upper limit (eg, Normal or Low). The same applies to the postbaseline value being below the lower limit with the baseline value being above the lower limit (eg, Normal or High).
- If the baseline value is missing, a postbaseline abnormality will always be considered as TE.

Proportion and incidence rate of treatment-emergent clinically important vital signs during intervention, as defined in Table 02, will be summarized for participants who had a baseline assessment and at least 1 postbaseline assessment for that vital sign.

Table 02: Treatment-Emergent Abnormality Categories for Vital Signs

	Post-baseline value outside of normal limit if:		
Vital Parameter	Abnormally low	Abnormally high	
Pulse (bpm)	A decrease from Baseline of ≥ 15 to a value ≤ 50	An increase from Baseline of ≥ 15 to a value ≥ 100	
Systolic BP (mmHg)	A decrease from Baseline of ≥ 20 to a value ≤ 90	An increase from Baseline of ≥ 20 to a value ≥ 180	
Diastolic BP (mmHg)	A decrease from Baseline of ≥ 15 to a value ≤ 50	An increase from Baseline of ≥ 15 to a value ≥ 105	
Respiratory rate (breaths per minute)	Any value < 10	Any value > 24	

BP = blood pressure;

The proportion and incidence rate of subjects who experienced treatment-emergent acute hypertension (systolic BP \geq 180 or diastolic BP \geq 110) at any time during Study 54135419TRD3013 or Study 54135419TRD4010 will be summarized.

The incidence rate is defined as the number of subjects who achieve the event divided by the time at risk. Time at risk is defined as time from initial administration of study intervention in Study 54135419TRD3013 until last visit date.

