- O Vital signs: blood pressure, pulse/heart rate, respiratory rate.
- P Vital signs will be measured at approximately 40 minutes after esketamine nasal spray dose and subsequently as clinically warranted until blood pressure values decline. Participants must be monitored by a healthcare professional until the participant is considered clinically stable and ready to leave the study site. If blood pressure remains elevated for a prolonged period of time, assistance should promptly be sought from practitioners experienced in blood pressure management. Participants who experience symptoms of a hypertensive crisis should be referred immediately for emergency care.
- ^q At an early study withdrawal visit or the safety follow-up visit (no esketamine nasal spray dose), vital signs will be performed according to usual practice.
- Vital signs performed for participants not administrating esketamine nasal spray at this visit.
- If the participant has nasal congestion on the dosing day, a nasal decongestant can be used to reduce congestion (but not within 1 hour before esketamine dosing) or the dosing day can be delayed (per the permitted visit window).

- ^t Esketamine nasal spray dosing and related safety-monitoring procedures MUST be performed LAST at all visits. Esketamine nasal spray must NOT be administered before all other visit assessments are completed.
- ^u The frequency of nasal treatment sessions may be individualized on even week visits from once weekly to every 2 weeks based on severity of depressive symptoms and at the discretion of the investigator. If participants show early signs of worsening of depressive symptoms after reduced treatment frequency, the treatment frequency can be changed back to once weekly at any visit.

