- Transient, primarily asymptomatic, increases in systolic and diastolic blood pressure (SBP and DBP) were observed following administration of esketamine nasal spray, with maximum mean changes typically observed within 40 minutes of dosing (consistent with peak plasma elevations) and mean blood pressure values subsequently returning to, or close to, predose values within the 1.5-hour postdose timepoint. The blood pressure elevations did not appreciably attenuate over time with continued administration. Few participants (<2% across studies/study phase) discontinued esketamine treatment due to increased blood pressure.
 - In clinical trials, increases in SBP and DBP over time were about 7 to 9 mm Hg in SBP and 4 to 6 mm Hg in DBP at 40 minutes post dose and 2 to 5 mm Hg in SBP and 1 to 3 mm Hg in DBP at 1.5 hours post dose in participants receiving esketamine nasal spray plus oral ADs. The frequency of markedly abnormal blood pressure elevations of SBP (≥40 mm Hg increase) ranged from 8% (<65 years) to 17% (≥65 years) and DBP (≥25 mm Hg increase) ranged from 13% (<65 years) to 14% (≥65 years) in participants receiving esketamine nasal spray plus oral AD. The incidence of increased SBP (≥180 mm Hg) was 3% and DBP (≥110 mm Hg) was 4%.

- Intranasal esketamine 84 mg was associated with an early, transient decline in cognitive function compared with placebo, which was restored to comparable levels in participants receiving either esketamine or placebo by 2 hours postdose. Transient reductions with esketamine were associated with early postdose sedation, as assessed by the Karolinska Sleepiness Scale, and the greater level of effort required to complete the test battery, as assessed using the Mental Effort Scale. The increases in sleepiness (at 40 minutes and 2 hours postdose) and the mental effort required (at 40 minutes postdose) returned to levels comparable to placebo by 4 and 2 hours postdose, respectively (Phase 1 study TRD1005).
- Treatment with esketamine nasal spray had no clinically meaningful effects on oxygen saturation as measured by pulse oximetry or on respiratory rate. There were no cases of

respiratory depression or intervention-emergent AEs that required cardiopulmonary resuscitation or other medical intervention reported in the Phase 2 or 3 studies.

- Results of the Phase 2 and Phase 3 studies indicate that there is no clinically meaningful effect of esketamine on body weight over short- or long-term administration.

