5.5. Criteria for Temporarily Delaying Enrollment or Administration of Study Intervention

If a participant cannot receive the esketamine nasal spray dose on the same day as the Week 32 visit in Study TRD3013, the participant may be enrolled in this study (TRD4010) as long as they continue their current SSRI/SNRI and receive their first dose of esketamine nasal spray within 14 days after the Week 32 visit date in Study TRD3013; Day 1 of this study will be the day of the esketamine nasal spray dose.

Administration of study intervention may be delayed if the participant has nasal congestion on the dosing day as described in Section 6.1.1, Esketamine Nasal Spray, or if the participant requires adjustment of blood pressure medication.

Appendix 4 provides guidance related to study conduct during the Coronavirus Disease 2019 (COVID-19) pandemic.

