9.4.5. Safety Analyses

All safety analyses will be made on the Safety/Efficacy Population.

Adverse Events

The verbatim terms used in the eCRF by investigators to identify adverse events will be coded using the Medical Dictionary for Regulatory Activities (MedDRA). Any AE occurring at or after the initial administration of study intervention through the day of last dose plus 30 days is considered to be intervention-emergent. All reported intervention-emergent adverse events will be included in the analysis. For each adverse event, the percentage of participants who experience at least 1 occurrence of the given event will be summarized.

Intervention-emergent AEs of special interest will be summarized separately grouped in the categories as described in Section 8.3.6.

Summaries, listings, or participant narratives may be provided, as appropriate, for those participants who die, who discontinue intervention due to an adverse event, or who experience a serious adverse event.

Clinical Laboratory Tests

Only clinically relevant changes in laboratory parameters that meet the definition of an AE during the study are reported by the investigator as AEs and these will be included in the all intervention-emergent AE analyses.

Vital Signs

Descriptive statistics of pulse/heart rate, respiratory rate, and supine blood pressure (SBP and DBP) values and changes from Study TRD3013 baseline will be summarized at each scheduled time point. The percentage of participants with values beyond clinically important limits will be summarized.

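### Table 02 vital-sign abnormalities are judged after baseline only on post-dose readings, so about half of the scheduled postbaseline readings cannot enter the participant-level count

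*SAP*

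**What the plan says.** SAP 5.6.3.2 (Vital Signs and Physical Examination Findings) states that the abnormality criteria "will be applied to baseline and postbaseline post-dose values". Table 02 then sets low and high limits for pulse, systolic and diastolic pressure and respiratory rate. The proportion and incidence rate of these abnormalities during intervention are summarized for "participants who had a baseline assessment and at least 1 postbaseline assessment for that vital sign".

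Pre-dose values have a descriptive role. The same section plans "descriptive statistics of pre-dose and post-dose pulse rate, blood pressure (systolic and diastolic) values and respiratory rate" with changes from pre-dose for each dosing day. If a reading lacks its pre-dose or post-dose label, "this will be derived from the vital sign assessment time and the esketamine administration time".

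A separate SAP paragraph counts participants with acute hypertension (systolic at least 180 or diastolic at least 110) occurring at any time in either study. It does not say which readings it uses.

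The protocol side is wider:
- Protocol 9.4.5: "The percentage of participants with values beyond clinically important limits will be summarized". No class of reading is excluded.
- The Schedule of Activities (1.3) requires vital signs before and after each dose. Footnote r adds readings at an end-of-study or withdrawal visit without a dose. Footnote q covers undosed withdrawal and follow-up visits: "no esketamine nasal spray dose), vital signs will be performed according to usual practice".
- Protocol 5.5 allows a dose to be delayed for nasal congestion "or if the participant requires adjustment of blood pressure medication".

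**The concern.** The Table 02 proportion and incidence rate are the plan's objective, participant-level statement about abnormal vital signs in a study whose primary objective is long-term safety. As written, they describe only the period shortly after a dose. A pressure, pulse or respiratory rate that is out of range before dosing, or at an undosed visit, cannot be an event. On a day when a dose is put off, there is a pre-dose reading and no post-dose one, so that day contributes nothing to Table 02 whatever the reading was.

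Two features add to this. The denominator is not restricted in the way the numerator is. And the low-pressure limits are tested at the time when, on average, the drug has raised pressure. A reader of the study report would probably take the table as covering vital-sign abnormalities throughout treatment, which it does not.

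**Working it through.** The plan gives no figure to reproduce here: the study has no hypothesis and no sample size calculation. The check has four parts.

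**1. Which readings can meet Table 02**

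| Reading | Collected? | Can meet Table 02 after baseline? |
|---|---|---|
| Post-dose, about 40 minutes, later as warranted | Yes | Yes |
| Pre-dose, dose then given | Yes | No |
| Pre-dose, dose then delayed or not given | Yes | No |
| Undosed end-of-study or withdrawal visit | Yes | No |
| Undosed safety follow-up visit | Yes | No (and possibly outside the during-intervention scope) |

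The rule for missing labels does not rescue the undosed visits, because it needs an administration time that they do not have.

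**2. Share of scheduled readings left out**

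Assume full 104-week participation in this study, one pre-dose and one post-dose reading per dose, and no dose at Week 104. The share left out is (doses + undosed visits) / (2 × doses + undosed visits).

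- Weekly dosing, 104 doses, 2 undosed visits (Week 104 and follow-up): (104 + 2) / (208 + 2) = 106/210 = 50.5%.
- Every 2 weeks, 52 doses, 1 undosed visit (Week 104, which also serves as follow-up): (52 + 1) / (104 + 1) = 53/105 = 50.5%.
- If follow-up lies outside the during-intervention scope: 105/209 = 50.2% and 52/104 = 50.0%.

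The answer is about half in each case.

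**3. What the post-dose restriction does to the low limits, on average**

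Protocol 2.2.3.4 gives mean rises of "about 7 to 9 mm Hg in SBP and 4 to 6 mm Hg in DBP at 40 minutes post dose". Subtracting them from the Table 02 low limits gives the pre-dose equivalents:

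- Systolic limit of 90: 90 − 7 = 83 and 90 − 9 = 81. The required fall of 20 becomes 27 to 29 mm Hg.
- Diastolic limit of 50: 50 − 4 = 46 and 50 − 6 = 44. The required fall of 15 becomes 19 to 21 mm Hg.
- At 1.5 hours the quoted mean rises are 2 to 5 systolic and 1 to 3 diastolic, giving 85 to 88 and 47 to 49.

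This is arithmetic on means. It does not by itself say how many participants are affected.

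**4. Whether the net effect on the low systolic row can be sized**

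Illustrative simulation; every input except the shift and the Table 02 limits is an assumption. Mean systolic 124, between-person SD 11, within-person SD 9, one baseline reading, 52 sessions, mean post-dose shift +8 (middle of 7 to 9). An event is at least one reading at or below 90 with a fall of at least 20. The varied input is the extra post-dose SD.

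| Extra post-dose SD (mm Hg) | At least one pre-dose event | At least one post-dose event |
|---|---|---|
| 0 | 7.5% | 1.3% |
| 5 | 7.8% | 3.1% |
| 8 | 7.8% | 7.5% |
| 10 | 7.6% | 13.5% |

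The pre-dose column estimates one quantity throughout; its variation is simulation noise. The post-dose count is well below the pre-dose count at SD 0 or 5, equal to it at about 8 and above it at 10. The documents do not give this SD. The protocol reports systolic rises of at least 40 mm Hg in 8% (under 65 years) to 17% (65 and over) of participants, which suggests wide individual variation, but it does not say whether those rises are from pre-dose or from baseline.

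**The case against.** The strongest reply is that the blood-pressure risk described in the documents is a transient rise after dosing, which post-dose criteria target, and that no hypotension signal is reported. That supports keeping the post-dose row. It does not explain why other readings taken during treatment are not judged at all.

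Other outputs cover part of the gap. Pre-dose values are summarized with minimum and maximum, clinically relevant changes must be recorded as adverse events, and SAP 5.6.1 summarizes doses not administered with reasons. This stands as mitigation. But a visit-level minimum is not a participant-level proportion, and adverse events depend on the investigator's judgment.

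Several stronger readings are tempting and should not be made:

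- *Pre-dose and undosed readings never count anywhere.* The documents support this only for Table 02. The acute-hypertension count is worded to cover any time in either study and may include pre-dose values. It has no low limit and does not cover pulse or respiratory rate.
- *The sessions most likely to be abnormal drop out.* Protocol 5.5 only permits a delay. It gives no blood-pressure threshold and no frequency.
- *Safety follow-up readings are wrongly omitted.* The summary is limited to the intervention period, so leaving out a visit 2 weeks after the last dose may be intended.
- *The SAP departs from the protocol without declaring it.* Protocol 9.4.5 defines neither limits nor readings, and Protocol 9 leaves specific details to the SAP. The SAP is narrower than the protocol sentence, but that is not clearly a change that had to be listed.

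**Conclusion.** The point holds for Table 02. After baseline the criteria reach only post-dose readings, so about half of the scheduled postbaseline readings, including the pre-dose reading on a day when the dose is not then given, cannot contribute to the participant-level proportion or incidence rate. The one-half figure assumes full participation and one reading on each side of each dose; later as-warranted post-dose readings would lower it.

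The denominator mismatch is real in the wording, since a participant with no post-dose reading would be classed as event-free. It is probably rare, because everyone in the analysis set receives at least one dose and a post-dose reading is scheduled with each.

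A reader might infer that the low-pressure rows are biased toward zero, or understated several-fold. The documents do not support that. Under one set of assumptions the gap is large, but it closes and then reverses as post-dose variability rises, and that variability is not reported. What can be said is that a reading taken at about 40 minutes, when mean systolic and diastolic pressure are raised, is a poor sole basis for the low rows. Adding the omitted readings can only leave the count of affected participants unchanged or raise it. No hypothesis test depends on the result.

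**What to change.** In SAP 5.6.3.2, apply the Table 02 criteria to all postbaseline readings during intervention and report three rows for each parameter:

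- (a) post-dose readings, kept as the acute-effect result;
- (b) pre-dose readings, including days when the dose was then not given, together with undosed visits;
- (c) any reading.

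Match the denominator of each row to the readings it uses, so that row (a) requires at least one post-dose reading. State that the acute-hypertension summary uses all readings.

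The cost is a few sentences of SAP text and two extra rows per table, from data already collected. The any-reading percentage will be the same as the post-dose one or somewhat higher.

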1. PROTOCOL SUMMARY

1.1. Synopsis

Open-label Long-Term Extension Study for Participants With Treatment-Resistant Major Depressive Disorder Who are Continuing Esketamine Nasal Spray Treatment From Study 54135419TRD3013

Open-label Extension Study to Assess Long-term Safety of Esketamine Nasal Spray

Esketamine hydrochloride (HCl) is referred to as JNJ-54135419-AAC. Esketamine is a nonselective, noncompetitive antagonist of the N-methyl-D-aspartate receptor (NMDAR), an ionotropic glutamate receptor. Through NMDAR antagonism, esketamine produces a transient increase in glutamate release leading to increases in α-amino-3-hydroxy-5-methyl-4-isoxazole propionic acid receptor (AMPAR) stimulation and subsequently to increases in neurotrophic signaling that restore synaptic function in these mood regulatory brain regions. Esketamine nasal spray is indicated for use in combination with a selective serotonin reuptake inhibitor (SSRI)/ serotonin-norepinephrine reuptake inhibitor (SNRI) to treat adults with treatment-resistant major depressive disorder (MDD). Esketamine nasal spray has also been approved by the United States Food and Drug Administration for MDD with acute suicidal ideation or behavior.

OBJECTIVES AND ENDPOINTS

Primary

Objectives

Primary	
To assess the long-term safety and tolerability of esketamine nasal spray in combination with an SSRI/SNRI in participants who have completed 32 weeks of esketamine nasal spray treatment in Study TRD3013.	Intervention-emergent adverse events (AEs), including intervention-emergent AEs of special interest Suicidal ideation and behavior: Columbia-Suicide Severity Rating Scale (C-SSRS)
Secondary	

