5.3.2.1. Analysis Methods

5.3.2.1.1. Primary Analysis

The verbatim terms used in the case report form by investigators to identify AEs will be coded using the Medical Dictionary for Regulatory Activities (MedDRA). Any AE occurring at or after the initial administration of study intervention in Study 54315419TRD3013 through completion the participant's 2-week safety follow-up visit in Study 54135419TRD4010 is considered to be treatment emergent. Serious AEs reported within 30 days after the last dose of study intervention in Study 54135419TRD4010 are also regarded as treatment emergent. If the event occurs on the day of the initial administration of study intervention, and either event time or time of administration are missing, then the event will be assumed to be treatment emergent. If the event date is recorded as partial or completely missing, then the event will be considered to be treatment emergent unless it is known to be prior to the first administration of study intervention based on partial onset date or resolution date. All reported treatment-emergent AEs will be included in the analysis. For each AE, the number, proportion and incidence rate of participants who experience at least 1 occurrence of the given event will be summarized. The incidence rate is defined as the numbers of participants who experience at least 1 occurrence of the AE divided by the time at risk. Time at risk is defined as time from initial administration of study intervention in Study 54135419TRD3013 until first occurrence of AE or until last dose of study intervention plus 30 days (if participant did not experience AE). To calculate time at risk if the start date of an AE is missing completely or partially, following imputation rule will be applied:

If the onset date of an adverse event is missing day only, it will be set to:

- i) First day of the month that the AE occurred, if month/year of the onset of AE is different than the month/year of initial dosing date of Study 54135419TRD3013
- ii) The day of initial dosing in Study 54135419TRD3013, if the month/year of the onset of AE is the same as month/year of the initial dose date and month/year of the AE resolution date is different
- iii) The day of initial dosing in Study 54135419TRD3013 or day of AE resolution date, whichever is earliest, if month/year of the onset of AE and month/year of the initial dosing date of Study 54135419TRD3013 and month/year of the AE resolution date are the same.

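### The acute hypertension rate (and apparently the Table 02 vital-sign rates) keeps counting person-time after a participant's first event, so it is slightly low and not comparable with the AE rate

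*SAP*

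**What the plan says.** SAP 5.6.3.2 plans a proportion and an incidence rate for treatment-emergent acute hypertension (systolic pressure at least 180 or diastolic at least 110) occurring "at any time during Study 54135419TRD3013 or Study 54135419TRD4010 will be summarized".

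- Rate: "The incidence rate is defined as the number of subjects who achieve the event divided by the time at risk".
- Denominator: "Time at risk is defined as time from initial administration of study intervention in Study 54135419TRD3013 until last visit date". There is no stop at the event.

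The same section also plans "Proportion and incidence rate of treatment-emergent clinically important vital signs during intervention", meaning the abnormalities in Table 02. It gives no separate time-at-risk definition for them.

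SAP 5.3.2.1.1 defines an incidence rate for adverse events with the same kind of numerator, participants with at least one occurrence. There, time at risk starts at the same first dose but runs "until first occurrence of AE or until last dose of study intervention plus 30 days", the second end point applying to participants without the event. The SAP gives no reason for treating the two outcomes differently.

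**The concern.** A participant who has had a first hypertensive reading cannot enter the numerator again, yet under 5.6.3.2 goes on adding to the denominator until the last visit. The quotient is then not a first-event rate.

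Blood-pressure elevation is a recognised effect of the drug (protocol 2.2.3.4), and long-term safety is the primary objective. A rate that leans low on this outcome is worth correcting. The report would also carry two safety rates with the same name and different person-time rules, which invites a comparison they cannot bear.

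**Working it through.** The documents give no acute hypertension rate for this study, so there is no figure to reproduce. The check is person-time algebra.

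**Inputs**
- Follow-up T: 32 weeks in TRD3013 plus up to 104 weeks here = 136 weeks = 952 days = 2.61 years (protocol 1.1). This is a maximum, because participation ends earlier where the drug becomes accessible locally.
- Proportion with the event p: protocol 2.2.3.4 gives 3% for systolic ≥180 and 4% for diastolic ≥110. The combined figure lies between 4% (full overlap) and 3% + 4% = 7% (no overlap).
- Mean fraction of follow-up elapsed at first event f: not in the documents. Assumed 0.5 (even timing) to 0.05 (early).
- Last visit: about last dose + 14 days (safety follow-up visit, protocol 1.3), so 30 − 14 = 16 days short of the AE end date.

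**Effect of not stopping at the event, end date held fixed**

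For N participants and E = pN events:
- SAP rate = E / (N·T)
- First-event rate = E / [E·f·T + (N−E)·T]
- Ratio, SAP to first-event = 1 − p(1−f)

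N cancels. The ratio is below 1 whenever anyone is followed after the event.

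| p | f | SAP rate per 100 patient-years | First-event rate | Understatement p(1−f) |
|---|---|---|---|---|
| 4% | 0.5 | 1.53 | 1.57 | 2.0% |
| 4% | 0.05 | 1.53 | 1.60 | 3.8% |
| 7% | 0.5 | 2.69 | 2.78 | 3.5% |
| 7% | 0.05 | 2.69 | 2.88 | 6.65% |
| 17% (illustration only) | 0.5 | 6.52 | 7.13 | 8.5% |
| 17% (illustration only) | 0.05 | 6.52 | 7.78 | 16.2% |

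A simulation with constant hazard over 136 weeks and p = 7% agrees. The true rate is 2.784 per 100 patient-years, the SAP definition gives 2.684, and stopping at the first event gives 2.782.

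**Comparison with the AE rule as written**

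The AE rule also runs event-free participants about 16 days longer, which enlarges its denominator:
- Ratio, SAP 5.6.3.2 rate to AE-rule rate = p·f + (1−p)(1 + 16/T)

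| Follow-up | p = 4%, f = 0.5 | p = 4%, f = 0.05 | p = 7%, f = 0.5 | p = 7%, f = 0.05 |
|---|---|---|---|---|
| 136 weeks | 0.996 | 0.978 | 0.981 | 0.949 |
| 58 weeks (assumed) | 1.018 | 1.000 | 1.002 | 0.970 |

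The two rules agree when p = 16 / [16 + (1−f)T]. That is 1.7% (f = 0.05) to 3.3% (f = 0.5) at 136 weeks, and 4.0% to 7.3% at 58 weeks. Below the break-even value, the vital-sign rate is the higher of the two.

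**The case against.** **Materiality.** The study is descriptive, with no hypothesis and 100 to 200 participants expected. At 4% of 100 to 7% of 200 there would be about 4 to 14 events. Exact Poisson 95% limits are about −73% to +156% around 4 events and −45% to +68% around 14, so a 2–7% shift is small beside sampling error. The proportion is reported alongside and is unaffected. Clinically relevant changes must also be recorded as AEs (protocol 8.2), and the AE rate already stops at first occurrence. This stands, and it is why the point is minor. It does not make the denominator right: the shift is systematic and avoidable.

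**Readings that go too far.** A reader might infer any of the following; the documents do not support them.
- *The rate is biased low beside the TEAE rates.* The AE rule's longer tail for event-free participants can cancel or reverse the difference at low incidence, as shown above. The understatement is certain only with the end date held fixed.
- *The SAP contradicts itself.* It gives two definitions for two outcomes, which is an inconsistency and not two rules for one outcome.
- *The understatement reaches the high teens.* Protocol 2.2.3.4 does quote 8–17% and 13–14%. Those are for rises of at least 40 mm Hg systolic and 25 mm Hg diastolic, change criteria that it calls markedly abnormal. They are not this endpoint.
- *The two weeks after the last dose cannot contain an event (14/966 = 1.4% more).* The post-dose restriction in 5.6.3.2 is attached to the abnormality criteria in Table 02. Acute hypertension is counted at any time in either study, and vital signs are scheduled at the safety follow-up visit.

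**Conclusion.** The point holds. As written, the acute hypertension rate divides first events by person-time that includes time after the first event, and the Table 02 rates appear to do the same. With the end of follow-up held fixed, the understatement is p(1−f): about 2–7% of the rate at a combined incidence of 4–7%, with f assumed between 0.05 and 0.5.

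A larger effect needs a higher cumulative incidence. That is possible: the completed studies averaged 611/1,708 = 0.36 patient-years per esketamine participant (protocol 2.2.3.4), against up to 2.61 years here. The documents give no such figure for this endpoint, however, and participants entering the extension have already tolerated 32 weeks of treatment.

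The rate is not comparable with the AE rate, because both the stopping rule and the end date differ. Within the ranges above, it falls between about 5% below and 2% above what the AE rule would give. Severity: minor.

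**What to change.** In SAP 5.6.3.2, for acute hypertension and every Table 02 rate, end time at risk at the participant's first qualifying reading. For participants without one, end it at a single stated end of observation that matches the window in which events are counted, for example the last vital-sign assessment eligible for that criterion.

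Ending at the last dosing visit would not serve for acute hypertension. It would add a third end date to the SAP and could leave an event counted at the safety follow-up visit outside its own time at risk.

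If the present definition is deliberate, the SAP should say why and give the rate a name that separates it from the AE incidence rate.

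The cost is one sentence in the SAP and a slightly less favourable rate. No new data are needed, since the dates of first dose, readings and visits are already used in the planned analyses.
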